4.1.4.2 Restrictions for lesion selection – BI 1387446

Lesions considered high risk for local complications should not be selected for injection. This includes tumours with

- encasement or suspected infiltration of major blood vessels,
- lesions located adjacent to vital structures which would be functionally impaired by swelling of injected lesion, e.g. trachea, carotid artery

4.1.4.3 Dose reductions and dose delays

As a general rule, any SAEs/AEs of \geq Grade 3 will result in a pause of treatment with BI 1387446 and/or ezabenlimab (BI 754091) until resolution to baseline or Grade 1.

In combination treatment arms, both drugs (BI 1387446 and ezabenlimab (BI 754091)) will be stopped, paused, or re-exposed together unless an AE can be attributed to either BI 1387446 or ezabenlimab (BI 754091). Only if a causal relationship to one trial drug can be unequivocally established, the other trial drug may be continued.

BI 1387446

Up to 2 dose reductions of BI 1387446 are allowed if the treatment pause due to an AE is \leq 12 weeks and the re exposure is considered clinically indicated by the Investigator.

Dose reductions will be only permitted to doses previously explored in lower dose levels. In case of re-occurrence or worsening of the same AE upon re-start of BI 1387446 at a lower dose, a second dose reduction of BI 1387446 is not permitted and BI 1387446 has to be permanently discontinued. Re-escalation to higher doses is not permitted. In case a third dose reduction would be required, treatment of that patient should be permanently discontinued. Treatment interruptions $>$ 12 weeks are only permitted for AEs not considered drug related and may be agreed on a case by case basis with the Sponsor.

Ezabenlimab (BI 754091)

Dose reductions or escalations of ezabenlimab (BI 754091) are not permitted. In case of adverse events, administration of ezabenlimab (BI 754091) should be delayed for up to 12 weeks to permit recovery from adverse events. Treatment interruptions $>$ 12 weeks are only permitted for AEs not considered drug related and may be agreed on a case by case basis with the Sponsor.

Infusion-related reactions

In the event of an infusion-related reaction \leq Grade 2, the infusion rate of ezabenlimab (BI 754091) may be decreased by 50% or interrupted until resolution of the event and re-initiated at 50% of the initial rate until completion of the infusion. In patients experiencing infusion-related reactions \leq Grade 2, subsequent infusions may be administered at 50% of the initial rate. If an infusion-related reaction is Grade 3 or higher in severity at any point during the study, treatment with ezabenlimab (BI 754091) has to be permanently discontinued.

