10.1.2 Management of immune-related adverse events

Regarding management of immune-related adverse events, grading and treatment, up-to-date published guidelines should be considered [e.g. [P19-00269](#)]. Only limited guidance on management of specific irAEs can be given here.

Please refer to published guidelines (e.g. ASCO guideline, Brahmer [P19-00269]) for details.

In general,

- For irAEs listed below, the guidance from [Section 4.1.4.3](#) is not considered applicable stating that only if a causal relationship to one trial drug can be unequivocally established, the other trial drug may be continued. On combination treatment both

drugs (BI 1387446 and ezabenlimab (BI 754091)) will be stopped, paused, or re-exposed together.

- Ezabenlimab (BI 754091) and BI 1387446 should be continued with close monitoring in case of grade 1 irAEs, with the exception of irAEs that may rapidly evolve into severe or fatal conditions (encephalitis of any grade, myocarditis of any grade, pneumonitis that is grade 1 but shows radiographic evidence of worsening – see detailed guidance below). A dose reduction of BI 1387446 may be considered, but is not required for the first occurrence of an irAE grade 1.
- For most Grade 2 irAEs, ezabenlimab (BI 754091) and BI 1387446 should be withheld and treatment with corticosteroids is commonly warranted, usually with an initial dose of 0.5 to 1 mg/kg prednisone / prednisone equivalent daily. Restart of therapy is commonly possible once symptoms and/or laboratory values have resolved to grade 1 or less, and on \leq 10 mg prednisone / prednisone equivalent per day. A dose reduction of BI 1387446 should be considered, but is not required for the first occurrence of an irAE, but is mandatory if the same irAE recurs upon rechallenge with BI 1387446.

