- For Grade 3 irAEs, ezabenlimab (BI 754091) and BI 1387446 has to be withheld, and treatment with high-dose corticosteroids (1-2mg/kg/d prednisone / prednisone equivalent) is usually warranted. Upon improvement, steroids should be tapered slowly over 4-6 weeks. Non-steroidal immunosuppressives (e.g. infliximab, mycophenolate mofetil) should be considered if no improvement or worsening occurs within the initial 48 to 72 hours. Upon recovery to grade 1 or less, and on \leq 10 mg prednisone / prednisone equivalent per day, restarting ezabenlimab (BI 754091) and BI 1387446 may be considered for selected irAEs, but caution is advised, in particular in patients with early-onset irAEs. Expert consultancy and agreement with medical monitor is recommended prior to restart of therapy. BI 1387446 should be administered at a reduced dose.
- Most Grade 4 irAEs warrant permanent discontinuation of ezabenlimab (BI 754091) and BI 1387446.
- Restart of therapy is commonly possible for endocrine irAEs regardless of grade once stable hormone replacement has been instituted and symptoms have recovered. In case of multiple hormone deficiencies, corticosteroid replacement has to precede thyroid hormone replacement therapy by several days in order to avoid adrenal crisis. A dose reduction of BI 1387446 may be considered, but is not required for the first occurrence of an endocrine irAE.

In case of prolonged steroid therapy or treatment with immunosuppressives consider the possibility of opportunistic infections and tuberculosis reactivation. Careful monitoring and consideration of administration of prophylactic antibiotics where appropriate are warranted.

Commonly, referral to experts in the management of organ-specific conditions is highly recommended, especially for irAEs grade 3 or grade 4, or irAEs where management is complex.

Ezabenlimab (BI 754091) and BI 1387446 should be permanently discontinued for immune related

- encephalitis, aseptic meningitis, transverse myelitis, or Guillain-Barre syndrome of any grade
- acquired thrombotic thrombocytopenic purpura of any grade
- myocarditis of any grade
- myasthenia gravis, peripheral neuropathy or autonomic neuropathy of grade ≥ 3
- myositis grade 2 with objective findings (see below), any myositis grade ≥ 3

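### When the same irAE recurs at Grade 2 after BI 1387446 was restarted at a reduced dose, Section 10.1.2 read literally requires a dose reduction while Section 4.1.4.3 requires permanent discontinuation

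*Protocol*

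**What the plan says.** Two parts of the Protocol govern what happens to BI 1387446 when an immune-related event comes back.

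- **Section 4.1.4.3 (dose reductions and delays), all AEs.** The general allowance reads "Up to 2 dose reductions of BI 1387446 are allowed if the treatment pause due to an AE is" no longer than 12 weeks. The recurrence rule follows. Its trigger is worded "In case of re-occurrence or worsening of the same AE upon re-start of BI 1387446 at a lower dose". Its stated consequence is that "a second dose reduction of BI 1387446 is not permitted and BI 1387446 has to be permanently discontinued". It applies to any type of AE and carries no grade limit.
- **Section 10.1.2 (irAE management), Grade 2 bullet.** It opens with "For most Grade 2 irAEs, ezabenlimab (BI 754091) and BI 1387446 should be withheld". On restart it says "A dose reduction of BI 1387446 should be considered, but is not required for the first occurrence of an irAE", and then that a reduction "is mandatory if the same irAE recurs upon rechallenge with BI 1387446".

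Section 10.1.2 switches off one part of 4.1.4.3 for the irAEs it lists: the rule that lets one drug continue when causality is clearly attributable to the other. It leaves the recurrence rule alone, and later repeats the cap of two reductions with a reference back to 4.1.4.3. Section 4.1.4.7 directs that irAEs be managed according to Appendix 10.1.

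**The concern.** Section 10.1.2 itself invites the investigator to consider a lower dose after a first Grade 2 irAE. An investigator who takes up that invitation puts the patient on the path that 4.1.4.3 addresses. If the same event then returns at Grade 2, one section says to reduce and the other says never to reduce again and to stop. Both cannot be followed.

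This is a stop-or-continue safety rule in a first-in-human trial, so sites should not have to choose between two texts. In Arm B the choice may reach ezabenlimab as well, because for the irAEs it lists 10.1.2 has both drugs stopped, paused or restarted together.

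For the analysis, whether a patient is recorded as stopping treatment because of the event, and how long treatment lasted, could depend on which section the site read.

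**Working it through.** The documents give no figure to reproduce, and no arithmetic applies. The check sets the two rules against each possible path.

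| Path | Section 10.1.2 | Section 4.1.4.3 | Result |
|---|---|---|---|
| Grade 2 irAE, restart at unchanged dose, same irAE recurs at Grade 2 | Reduction required | Recurrence rule not triggered, since it needs a restart at a lower dose; cap not reached if there was no previous reduction | Compatible |
| Grade 2 irAE, restart at reduced dose, same irAE recurs at Grade 2, type not on a stop list | Reduction required, read literally | Second reduction barred; permanent stop | **Conflict** |
| Recurrence at Grade 3 or higher | Permanent stop | No contrary instruction; stop if the restart was at a lower dose | Compatible |
| Recurrent colitis of any grade; recurrent hepatitis or nephritis of Grade 2 or higher | Permanent stop | No contrary instruction; stop if the restart was at a lower dose | Compatible |

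Only the second row conflicts. Could anything else in the Protocol settle it?

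1. **The cap of two reductions.** It does not. In the second row one reduction has been used, so the cap alone would allow another. Only the recurrence rule forbids it.
2. **The carve-out in 10.1.2.** It covers the single-drug causality rule only, so the recurrence rule still applies to irAEs.
3. **The discontinuation list in Section 3.3.4.1.** It names the need for more than two reductions, and irAEs requiring a stop under 10.1.2. It does not name the recurrence rule of 4.1.4.3.
4. **The sponsor-discussion clause in 10.1.2.** It covers continuing despite guidance to stop. It does not say whether a stop applies here.
5. **Comparable wording elsewhere.** For LVEF decline, Section 5.2.5 says expressly that the recurrence must follow re-exposure at a reduced dose. The Grade 2 bullet has no such qualifier.

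**Which events remain.** Besides the stop rules in the table, 10.1.2 requires a permanent stop at Grade 2 for autoimmune haemolytic anaemia and for myositis with objective findings. It allows treatment to continue through Grade 2 rash and has a separate bullet for endocrine events. What remains includes Grade 2 pneumonitis, uveitis, peripheral or autonomic neuropathy, and arthritis.

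**Where it would show in the analysis.** SAP Section 7.8.1 tabulates AEs leading to discontinuation and AEs leading to dose reduction separately and provides a listing of each; SAP Section 7.7 summarises treatment duration and cumulative dose. AE tables count patients, not events. A patient already reduced for the first episode may therefore already be in the dose-reduction table under the same term, and in that case the visible difference would lie in the discontinuation table, the listings and exposure.

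**The case against.** The best answer is that the two rules complement each other. The Grade 2 sentence in 10.1.2 contrasts first occurrence with recurrence. It can be read as saying that a reduction which was optional the first time is no longer optional the second time. That describes the patient restarted at an unchanged dose, while 4.1.4.3 describes the patient restarted lower. Section 10.1.2 also points back to 4.1.4.3 on dose reductions and calls itself limited guidance, so an express prohibition in the main text could be taken to qualify it.

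This reading is plausible and may be what was meant. It is not what is written: the rechallenge has no dose attached, no order of precedence is given, and 4.1.4.7 sends sites to the appendix. What stands of the objection is that the conflict is confined to one path.

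Three stronger readings are tempting and are not supported.

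- **That the sections conflict for any recurrent irAE.** The mandatory-reduction sentence sits only in the Grade 2 bullet. For recurrences of Grade 3 or higher and for the named recurrences, 10.1.2 itself requires stopping.
- **That the restart after a Grade 3 irAE creates a second written conflict.** Section 10.1.2 does say of that restart that "BI 1387446 should be administered at a reduced dose". But the Grade 3 bullet has no rule for reducing again on recurrence. Carrying the Grade 2 sentence over to an event that began at Grade 3 is inference.
- **That late-DLT follow-up would be distorted.** Most Grade 2 events are not DLTs under Section 4.1.4.4. The SAP's analysis of DLTs over the whole on-treatment period (Section 7.4.4) is only optional. No effect is shown.

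**Conclusion.** The point holds in a narrow form. For a Grade 2 irAE outside the specific stop rules of 10.1.2, after restart of BI 1387446 at a reduced dose and recurrence of the same irAE at Grade 2, the literal texts of 10.1.2 and 4.1.4.3 cannot both be obeyed, and nothing states which prevails.

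The number of patients affected cannot be derived from the documents and may be small. The consequence is possible, not demonstrated: sites may differ in stopping or reducing, with matching inconsistency in the discontinuation and dose-reduction outputs and in exposure.

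The primary MTD analysis is essentially unaffected. It uses DLTs from Cycle 1 and the Cycle 2 Day 1 cardiac scan. A patient who misses a dose in that period without a DLT is not evaluable (Section 3.3.4.4). A withheld, recovered, restarted and recurrent event is unlikely to fit within three weeks.

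The conclusion assumes the Grade 2 sentence is taken at its literal wording; if the sponsor meant only a reduction not made at first occurrence, the text needs to say so. SAP Section 4 reports that development has been terminated, which limits how many patients a change can still reach. Section 3.3.5 nevertheless keeps consented patients on the treatment plan.

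**What to change.** Reconcile Sections 4.1.4.3 and 10.1.2 so that one stated rule covers recurrence of the same irAE after restart at an unchanged dose and after restart at a reduced dose. State the restart dose explicitly in the Grade 2 bullet of 10.1.2, and cross-refer that bullet to the recurrence rule in 4.1.4.3. Which rule applies is the sponsor's clinical decision, and this review takes no position on it.

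The cost is protocol wording; no design, sample size or analysis changes. If no further amendment is planned, the trial report can use the listings already specified in SAP Section 7.8.1, with the dosing records, to identify any patient on this path and state how the recurrence was handled.

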4.1.4.4 Dose limiting toxicity

DLTs will be recorded throughout the trial. Only DLTs starting in the first cycle of monotherapy (Arm A), or during the first cycle of BI 1387446 in combination with ezabenlimab (BI 754091) (Arm B) are required for dose-escalation decisions made by the SMC. DLT information from later cycles will be taken into consideration if applicable.

Any of the following AEs will be classified as DLTs unless unequivocally due to underlying malignancy or an extraneous cause:

- A) Hematologic toxicity
 - 1) any grade 5 toxicity
 - 2) neutropenia grade 4 lasting for $>$ 5 days
 - 3) neutropenia grade \geq 3 with documented infection
 - 4) febrile neutropenia
 - 5) thrombocytopenia grade 4
 - 6) thrombocytopenia grade 3 with concomitant bleeding grade \geq 2 (i.e. bleeding requiring intervention)

B) Grade 4 anaemia

C) Non-haematological toxicity

- 1) AST or ALT >3 times ULN and concurrent total bilirubin >2 times ULN without initial findings of cholestasis (e.g. findings consistent with Hy's law or the FDA definition of potential DILI)
- 2) AST or ALT elevation grade ≥ 4
- 3) CRS grade ≥ 3
- 4) Any other \geq Grade 3 non-haematologic toxicity with the following exceptions:
 - a. Grade 3 irAE that resolves to \leq Grade 1 or to baseline with immunosuppressive therapy within 2 weeks
 - b. Grade 3 fatigue that persists <7 days
 - c. Grade 3 rash that resolves to \leq Grade 1 within 2 weeks
 - d. Grade 3 or 4 elevation in serum amylase and/or lipase that is not associated with clinical or radiographic evidence of pancreatitis
 - e. Grade 3 electrolyte abnormality that lasts <72 hours, is not clinically complicated, and resolves spontaneously or responds to conventional medical intervention
 - f. Grade 3 nausea or vomiting that lasts <48 hours, and resolves to \leq Grade 1 either spontaneously or with conventional medical intervention
 - g. Alopecia
 - h. Grade 3 endocrine disorders (thyroid, pituitary, and/or adrenal insufficiency) that are managed with or without systemic corticosteroid therapy and/or hormone replacement therapy, and the patient is asymptomatic.
 - i. Grade 3 tumour flare syndrome
- 5) Pneumonitis Grade 2
- 6) Any Grade 2 related uveitis, eye pain, or blurred vision that does not respond to topical therapy and does not improve to Grade 1 severity within 2 weeks or requires systemic treatment
- 7) Any Grade ≥ 2 toxicity that persists and results in a delay of >14 days of Cycle 2 Day 1.

The frequency, time to onset, and severity of toxicities, as well as the success of standard medical management and dosing interruptions/delays, will be analysed to determine if a given toxicity not listed above should be considered a DLT for dose escalation purposes.

Late DLTs are AEs that meet the DLT criteria but occur on treatment after the completion of the initial MTD evaluation period (Arm A and B: Cycle 1, including echocardiographic/MUGA scan measurements acquired on Day 1 of Cycle 2 and related findings). If any late DLT is reported during dose escalation, the BLRM will be rerun using all DLTs, and updated results will be reviewed in the SMC meeting to recommend the next dose level and cohort size.

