The trial will be monitored by a SMC which will convene for each dose escalation decision. The SMC will assess for each dose cohort if dose escalation to the next dose level is possible based on DLTs in the MTD evaluation period, AEs, and safety laboratory data. DLTs and AEs reported in later cycles of patients enrolled in previous dose cohorts will be considered in addition. After the patients in a dose cohort have either experienced a DLT or have been observed for at least the MTD evaluation period without experiencing a DLT, the BLRM will be updated with the newly accumulated data. In particular, during dose escalation, the BLRM will be evaluated after the occurrence of each DLT before enrolling any further patients.

The SMC may recommend stopping the dose escalation after the criterion for MTD (refer to [Section 7](#)) is fulfilled. The RP2D will not exceed the MTD and will not exceed the highest dose investigated during dose escalation.

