10. APPENDICES

10.1 IMMUNE-RELATED ADVERSE EVENTS

10.1.1 Immune related adverse events of special interest

Table 10.1.1: 1 Immune-related adverse events of special interest

Immune-related adverse events of special interest
Pneumonitis (reported as an AESI if \geq Grade 2) 
• Acute interstitial pneumonitis• Interstitial lung disease• Pneumonitis
Colitis (reported as an AESI if \geq Grade 2 or any grade resulting in dose modification or use of systemic steroids to treat the AE) 
• Intestinal obstruction• Colitis• Colitis microscopic• Enterocolitis• Enterocolitis haemorrhagic• Gastrointestinal perforation• Necrotizing colitis• Diarrhoea
Endocrine (reported as an AESI if \geq Grade 3 or \geq Grade 2 and resulting in dose modification or use of systemic steroids to treat the AE) 
• Adrenal insufficiency• Hyperthyroidism• Hypophysitis• Hypopituitarism• Hypothyroidism• Thyroid disorder• Thyroiditis• Hyperglycaemia, if \geq Grade 3 and associated with ketosis or metabolic acidosis
Endocrine (reported as an AESI) 
• Type 1 diabetes mellitus (if new onset)

Table 10.1.1: 1

Immune-related adverse events of special interest (cont.)

Immune-related adverse events of special interest
Hematologic (reported as an AESI if \geq Grade 3 or any grade resulting in dose modification or use of systemic steroids to treat the AE)

• Autoimmune haemolytic anaemia• Aplastic anaemia• Thrombotic thrombocytopenic purpura• Idiopathic (or immune) thrombocytopenia purpura• Disseminated intravascular coagulation• Haemolytic-uraemic syndrome• Any Grade 4 anaemia regardless of underlying mechanism
Hepatic (reported as an AESI if \geq Grade 2, or any grade resulting in dose modification or use of systemic steroids to treat the AE)

• Hepatitis• Autoimmune hepatitis• Transaminase elevations (ALT and/or AST)
Cytokine Release Syndrome (reported as an AESI if \geq Grade 2)
Infusion Reactions (reported as an AESI for any grade)

• Allergic reaction• Anaphylaxis• Serum sickness• Infusion reactions• Infusion-like reactions
Neurologic (reported as an AESI for any grade)

• Autoimmune neuropathy• Guillain-Barre syndrome• Demyelinating polyneuropathy• Myasthenic syndrome

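### Grade 2 pneumonitis is a listed DLT, but read literally a grade 3 immune-related pneumonitis that resolves within 2 weeks is not, so the same event can be classified two ways

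*Protocol*

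**What the plan says.** The non-haematological DLT list in Protocol 4.1.4.4 (part C) contains four relevant items. All apply "unless unequivocally due to underlying malignancy or an extraneous cause".

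- **C4:** any other non-haematological toxicity of grade 3 or higher, with exceptions. Exception a covers a grade 3 immune-related event that resolves to grade 1 or lower "or to baseline with immunosuppressive therapy within 2 weeks". Pneumonitis is not carved out.
- **C5:** "5) Pneumonitis Grade 2", with no condition on duration or treatment.
- **C6:** three kinds of treatment-related ocular event at grade 2 (blurred vision, uveitis, eye pain), counted when topical treatment fails and the event "does not improve to Grade 1 severity within 2 weeks or requires systemic treatment".
- **C7:** grade 2 or higher "toxicity that persists and results in a delay of >14 days of Cycle 2 Day 1".

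The paragraph after the list says that features such as frequency, severity and success of management will be analysed "to determine if a given toxicity not listed above should be considered a DLT for dose escalation purposes". Table 10.5: 4 repeats C4 to C7 in its 1426-0001 column. In Table 10.1.1: 1 the pneumonitis entry begins "Pneumonitis (reported as an AESI if" and sets the threshold at grade 2 or higher. Protocol 10.1.2 stops both drugs permanently for grade 3 or 4 pneumonitis, with continuation only in rare cases discussed with the sponsor.

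**The concern.** The list counts the milder form of a toxicity without exception and can exempt the more severe form. It looks like a missing sign rather than a choice. The same list writes 'grade 2 or higher', 'grade 3 or higher' or 'grade 4 or higher' where that is meant (neutropenia with infection, transaminases, CRS, C7). The AESI table uses grade 2 or higher for pneumonitis. An event that normally ends treatment is an odd one to exempt.

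The number of patients with DLTs is one primary endpoint, and DLTs are the outcome that the Bayesian logistic regression model (BLRM) uses for the other, the MTD. A classification also triggers action: Protocol 3.1 says that during escalation "the BLRM will be evaluated after the occurrence of each DLT before enrolling any further patients". An event not classified as a DLT does not trigger that re-run. If sites can read the list two ways, the count depends on who classifies the event.

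**Working it through.** **1. The items side by side** (Cycle 1 pneumonitis, after the general exclusion for malignancy or extraneous cause).

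| Event | Item | DLT as written? |
|---|---|---|
| Grade 2, any course | C5 | Yes |
| Grade 3, immune-related, resolved to grade 1 or lower, or baseline, on immunosuppression within 2 weeks | C4, exception a | No, unless C5 is held to be met during recovery |
| Grade 3, not resolved in time or not immune-related | C4 | Yes |
| Grade 4 | C4 | Yes |

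C6 has the same shape. A grade 2 uveitis that needs systemic treatment is a DLT; a grade 3 immune-related uveitis that resolves on immunosuppression within 2 weeks falls under the exception, although Protocol 10.1.2 stops both drugs at grade 3.

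**2. Other routes to a DLT.** C7 needs a toxicity that persists and delays Cycle 2; this one has resolved. The analysis after the list could reclassify it, but the outcome is a judgement and the wording concerns toxicities that are not listed. SAP 7.4.4 uses DLT data only, so it does not recover an event that was never classified as a DLT.

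**3. What happens to the patient.** If a Cycle 1 dose or the Cycle 2 Day 1 echocardiography/MUGA scan is missed, the patient is not evaluable and is replaced unless the safety monitoring committee (SMC) decides otherwise (Protocol 3.3.4.4; SAP 6.3 and Table 7.4.1: 1). If all Cycle 1 doses and that scan were done, the patient stays in the MTD set without a DLT (SAP 6.4). After replacement, both routes give 0/3 where counting gives 1/3.

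**4. The protocol's own scenarios (10.5).** One DLT among three patients in the first Arm A cohort leaves no planned dose (Scenario 03); none allows escalation (04). At the second level 1/3 bars escalation (05) and 1/6 reopens it, to 200 µg (06).

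**5. Illustrative joint BLRM.** Model and priors are those of Protocol 7 and Table 7: 1, with the second prior argument read as a standard deviation. For BI 1387446, logit(π) = log α + β log(d/d\*). The quantity is P(π ≥ 0.33 given data), which must be below 0.25. Assumed because redacted: d\* of 400, 800 or 1200 µg; trial 1381-0001 data of 0/6, 0/20 or 0/56; doses doubling from 50 µg.

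Check against the plan: 1/1 at 50 µg gives 0.657 with d\* = 800 µg (stated: 0.656, Scenario 02). Scenarios 03 to 06 are also reproduced. The match at 800 µg is a calibration, since d\* is unknown.

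Arm A, 0/3 at 50 µg, overdose probability at 200 µg:

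| Data at 100 µg | d\* 400 | d\* 800 | d\* 1200 |
|---|---|---|---|
| 0/3 (event not counted) | 0.072 | 0.033 | 0.023 |
| 1/3 (event counted) | 0.390 | 0.298 | 0.262 |
| 1/6 (counted, then a clean cohort) | 0.240 | 0.160 | 0.132 |

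With d\* of 1500 µg, 1/3 gives 0.243 and would not bar 200 µg. That value fits the protocol less well: it gives 0.638 for Scenario 02 and contradicts Scenario 05.

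**6. Arm B.** With 3-patient Arm A cohorts one level ahead and no DLT there, an event at level 1 gives 0.005–0.035 uncounted and 0.050–0.164 counted at 100 µg. An event at level 2 gives 0.003–0.038 and 0.031–0.141 at 200 µg. Neither bars escalation. Over 9 Arm B data states × 9 input sets = 81, counting bars the next dose in 8. In 2 + 1 + 3 = 6 of those, Arm A already has a DLT. Uncounted, the largest value is 0.178.

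**7. Final-type check.** Arm A, 0/3 at each lower dose and r/6 at a top dose of 200, 400 or 800 µg (1381-0001 data 0/20): r = 0 gives 0.001–0.014, r = 1 gives 0.027–0.105, r = 2 gives 0.135–0.346. Arm B, r/6 at 400 µg with 0/3 at lower Arm B doses and at five Arm A doses: r = 1 gives 0.002–0.025, r = 2 gives 0.014–0.123.

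**8. Frequency.** Pneumonitis is among the immune-related events seen on ezabenlimab alone, but the only one of grade 3 or higher in 56 patients was an AST increase (Protocol 1.2.2). For 0/56 the one-sided 95% upper bound is 1 − 0.05^(1/56) = 0.052. The rate with BI 1387446 is unknown.

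**The case against.** The list is disjunctive. The exception sits inside C4 and does not limit C5, so a grade 3 event that resolves arguably meets C5 on its way down. The analysis of unlisted toxicities is stated as something that will be done, so only its outcome is open. Escalation does not rest on the count alone: the SMC also weighs AEs and safety laboratory data (Protocol 3.1), and pneumonitis of grade 2 or higher is an AESI reportable within 24 hours. SAP 7.8.1 already tabulates AESIs and immune-related AEs by highest grade in the treated set, so replaced patients appear. The first-cohort scenarios are history, because Arm B had already opened by protocol version 5.0. In Arm B, where ezabenlimab is given, one event seldom changes a decision.

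All of this stands, and it limits the finding. Exclusion is the literal default, not a certainty, and the toxicity would not go unseen. None of it makes the event a DLT by rule, and the argument about passing through grade 2 shows why the text needs settling. A reader might also infer that severe pneumonitis as a class escapes the DLT definition. It does not: grade 4 counts, and so does grade 3 that does not resolve in time or is not immune-related.

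**Conclusion.** The wording is wrong as it stands, and it feeds the primary endpoints. Confidence in that is high: the grade 2-only text appears in both 4.1.4.4 and Table 10.5: 4, while the sign survives elsewhere in the same list. The consequence is less certain, because two routes could still lead to the event being counted.

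The size is small. In Arm A one uncounted event can permit an escalation that would otherwise need another cohort. This rests on the assumed reference dose and 1381-0001 data, but Scenarios 05 and 06 show the same pattern without those assumptions. A reader might infer that the MTD is biased or will be set too high. The documents do not support that: no such event is documented, and in the final-type cases checked one uncounted event alone does not move the MTD. In Arm A it could do so for some inputs if another DLT occurred at the same dose; in the Arm B case checked even two events did not close the dose. It should be corrected, but it does not undermine the trial.

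**What to change.** **Wording**, for the definition and any reuse of it:

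- C5: *Pneumonitis Grade ≥ 2*.
- C6: begin *Any Grade ≥ 2 related uveitis, eye pain, or blurred vision*, conditions unchanged.
- C4, exception a: *Grade 3 irAE (other than pneumonitis, uveitis, eye pain or blurred vision, for which items 5 and 6 apply) that resolves…*
- Make the same changes in the 1426-0001 column of Table 10.5: 4 only. The 1381-0001 column describes another trial, which shares the C6 wording.

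**Check before the final MTD analysis**, the main action now that development has ended (SAP 4). From the planned AESI and immune-related AE outputs, identify grade 3 pneumonitis and ocular events of the C6 type in the MTD evaluation period, including in replaced patients. Use the all-AE table for eye pain and blurred vision, which Table 10.1.1: 1 does not name. Apply the period as derived in SAP 5.1, because it extends to 90 days after the last dose when Cycle 2 is not given. If there are none, say so in the report. If there is one, show the joint BLRM with and without it as a DLT.

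**Cost:** three short edits, repeated in one table column, and one review of data already collected. Slightly more events could count as DLTs. An extra model run is needed only if an event is found.
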